7.1.2.5. Maximum Number of Inhalations Taken In a 24-Hour Period

Summary descriptive statistics of the maximum number of inhalations taken in a 24-hour period will be presented overall and by CAE status and by CAE severity.

Data listings for each parameter of albuterol use will be presented by patient.

7.2. Inhalational Flow Values

7.2.1. Inhalational Flow Values Definitions

Study Day X and Week Y inhalational flow values are defined as follows:

Study Day X Inhalational Flow Values: The inhalational flow values for Study Day X are computed using the set of inhalations taken by the patient on Study Day X . Among these inhalations, the inhalation with the highest MIF value is considered the 'Study Day X Inhalation'. The Study Day X MIF, inhalational volume, inhalation duration, and time to MIF values are those of the identified 'Study Day X Inhalation'. If there was no albuterol use on Study Day X ,

then the closest preceding nonmissing Study Day Inhalation' is used as the 'Study Day *X* Inhalation' and the inhalational flow values for Study Day *X* are assigned accordingly.

Week *Y* Inhalational Flow Values: The inhalational flow values for Week *Y* are computed using the set of inhalations taken by the patient during a given week on the study. Among these inhalations, the inhalation with the highest MIF inhalation flow value is considered the 'Weekly *Y* Inhalation'. The Weekly *Y* MIF, inhalational volume, inhalation duration, and time to MIF values are those of the identified 'Weekly *Y* Inhalation'.

Note, if a patient never used the ABS eMDPI during the study or download of a given ABS eMDPI device was not successful, study day and weekly inhalational flow values will be missing.

7.2.2. Analysis Methods for Inhalational Flow Values

7.2.2.1. Actual and Change from Baseline in Study Day *X* Inhalational Flow Values Prior to the Peak of a CAE

Among patients who experienced a CAE, summary descriptive statistics of the actual inhalational flow values and change from baseline in daily inhalational flow values for MIF, inhalational volume, inhalation duration, and time to MIF at 1 day (eg, the 24-hour period on the day prior to the date of the CAE symptom peak) and at 3, 5, 7, 10, 14, and 21 days preceding the peak of a CAE will be presented for all CAEs and by moderate CAEs and severe CAEs.

In this analysis, among patients experiencing more than 1 CAE, the subsequent CAEs can be considered a separate CAE distinct from the first (preceding) CAE provided the patient exhibited at least 1 day of baseline albuterol use after the first (preceding) CAE's date of symptom peak and prior to the subsequent CAE's date of symptom peak. For patients who experience multiple CAEs (eg, 3), for a given number of days preceding a CAE (eg, 7 days), if the (eg, third) CAE overlaps with the time period of the preceding (eg, second) CAE, the CAE (eg, third CAE) should not be included in the analysis.

Summary descriptive statistics of the actual inhalational flow values and change from baseline in daily inhalational flow values for MIF, inhalational volume, inhalation duration, and time to MIF will be presented for the first occurrence of a single day's albuterol use exceeding (i) 4 inhalations, (ii) 12 inhalations, and (iii) 20 inhalations, overall and by CAE status and by CAE severity.

In addition, summary descriptive statistics of the maximum change from baseline in daily inhalational flow values for MIF, inhalational volume, inhalation duration, and time to MIF will be presented overall and by CAE status and by CAE severity.

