4.2.3. Inhalational Flow Values

The baseline inspiratory flow values are computed using the set of inhalations taken by the patient during study day 1 through day 14. Among these inhalations, the inhalation with the highest maximal inhalation flow (MIF) value is considered the ‘baseline inhalation’. The baseline MIF, inhalational volume, inhalation duration, and time to MIF values are those of the identified ‘baseline inhalation’. If no inhalations were taken during study day 1 through study day 14, the ‘baseline inhalation’ is the first available inhalation after study day 14.

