4.2.4. Total Daily Steps

Baseline TDS is the average number of daily steps a patient completes, computed using the daily steps recorded during the first 14 days of study participation (study day 1 through study day 14). The average will be calculated as the sum of the daily TDS divided by the number of days with nonmissing TDS. If no step data are available for study day 1 through study day 14, the ‘baseline TDS’ is the first available TDS after study day 14.

Baseline TDS are computed for those patients in the ankle accelerometry analysis set.

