7.3.2. Analysis Methods for Total Daily Steps

7.3.2.1. Actual and Change from Baseline in Study Day *X* Total Daily Steps Prior to the Peak of a CAE

Among patients in the ankle accelerometry cohort who experienced a CAE, summary descriptive statistics of the actual TDS and change from baseline in TDS 1 day (eg, the 24-hour period on the day prior to the date of the CAE symptom peak) and at 3, 5, 7, 10, 14, and 21 days preceding the peak of a CAE will be presented for all CAEs and by moderate CAEs and severe CAEs.

In this analysis, among patients experiencing more than 1 CAE, the subsequent CAEs can be considered a separate CAE distinct from the first (preceding) CAE provided the patient exhibited at least 1 day of baseline albuterol use after the first (preceding) CAE's date of symptom peak and prior to the subsequent CAE's date of symptom peak. For patients who experience multiple CAEs (eg, 3), for a given number of days preceding a CAE (eg, 7 days), if the (eg, third) CAE overlaps with the time period of the preceding (eg, second) CAE, the CAE (eg, third CAE) should not be included in the analysis.

Among patients in the ankle accelerometry cohort summary descriptive statistics of the actual TDS and change from baseline in TDS will be presented for the first occurrence of a single day's albuterol use exceeding (i) 4 inhalations, (ii) 12 inhalations, and (iii) 20 inhalations, overall and by CAE status and by CAE severity.

In addition, summary descriptive statistics of the maximum change from baseline in TDS will be presented overall and by CAE status and by CAE severity. For patients who experienced a CAE, the maximum change from baseline in TDS is the maximum change from baseline in TDS among the days prior to the exacerbation.

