7.4.2. Analysis Methods for Sleep Disruption Indices

7.4.2.1. Actual and Change from Baseline in Study Day X Sleep Disruption Indices Prior to the Peak of a CAE

Among patients in the wrist accelerometry cohort who experienced a CAE, summary descriptive statistics of nighttime average sleep latency time, longest nighttime wake episode, and total time awake at night and change from baseline in these three measures of SDI at 1 day (eg, the 24-hour period on the day prior to the date of the CAE symptom peak) and at 3, 5, 7, 10, 14 and 21 days preceding the peak of a CAE will be presented for all CAEs and by moderate CAEs and severe CAEs.

Summary descriptive statistics of nighttime average sleep latency time, longest nighttime wake episode, and total time awake at night and change from baseline in these three measures of SDI will be presented for the first occurrence of a single day's albuterol use exceeding (i) 4 inhalations, (ii) 12 inhalations, and (iii) 20 inhalations overall, and by CAE status and by CAE severity.

In addition, summary descriptive statistics of the maximum daily change from baseline nighttime average sleep latency time, longest nighttime wake episode, and total time awake at night will be presented overall and by CAE status and by CAE severity.

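### In the SAP's threshold-day tables, the first day above 4, 12 or 20 inhalations may lie inside the Day 1–14 baseline it is compared with, and MIF sets a one-day best against a 14-day best

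*SAP*

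**What the plan says.** **Baseline.** For flow, SAP 4.2.3 states: "The baseline inspiratory flow values are computed using the set of inhalations taken by the patient during study day 1 through day 14". Within that set, "the inhalation with the highest maximal inhalation flow (MIF) value is considered the" baseline inhalation, and its volume, duration and time to MIF go with it. A fallback to the first later inhalation applies "If no inhalations were taken during study day 1 through study day 14". For steps, SAP 4.2.4 takes an average "computed using the daily steps recorded during the first 14 days of study participation", divided by the number of nonmissing days. SAP 4.2.5 averages each sleep measure over the same 14 days.

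**Day value.** SAP 7.2.1 uses a single-day best for flow: "Among these inhalations, the inhalation with the highest MIF value is considered the" value for that study day. On a day without use, the closest preceding value is carried forward.

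**Threshold-day tables.** SAP 7.2.2.1 reports, beside the actual values, changes relative to "baseline in daily inhalational flow values for MIF, inhalational volume, inhalation duration, and time to MIF will be presented for the first occurrence", meaning the first day above 4, 12 and 20 inhalations. SAP 7.3.2.1 says "change from baseline in TDS will be presented for the first occurrence of a single" day above each threshold, and SAP 7.4.2.1 says "change from baseline in these three measures of SDI will be presented for the first occurrence of a single" day above each. All three are shown overall, by CAE status and by severity.

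None of these sections requires the crossing day to fall after Day 14, or takes it out of the baseline. A two-week guard exists in SAP 7.5.2.1, but only for the comparison of the two weeks before a CAE.

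**The concern.** A change from baseline should set a day against a reference that does not contain it. Here a patient who first exceeds a threshold on, say, Day 3 is compared with an average, or a best value, that includes Day 3. For steps and sleep this pulls the change toward zero. For MIF it caps the change at zero. Patients who cross after Day 14 are not affected in this way, so one table would mix two different quantities.

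MIF has a second problem that does not depend on overlap. The baseline is the best of up to 14 days of inhalations and the crossing-day value is the best of one day, so the change leans downward even when breathing has not altered.

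At stake is how these tables are read. They are meant to show what flow, activity and sleep look like when albuterol use first becomes high, with patients split by CAE status. Overlap should be commoner in habitual heavy users. In the cohort cited in protocol 3.3, exacerbating patients used about three times as much albuterol (5.5 / 1.83 = 3.0), so the effect may differ between the CAE columns.

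**Working it through.** **Inputs.** Baseline and day-value rules: SAP 4.2.3–4.2.5 and 7.2.1. Daily use: protocol 3.3, a different cohort, with means of 5.5 (SD 9.7) and 1.83 (SD 3.3) actuations per day with and without exacerbation. Share with a CAE: 20–25%, SAP 2.3. The planning figures there reproduce (400 × 0.90 = 360; 0.20 × 360 = 72; 0.25 × 360 = 90) and are not affected by this point. The plan gives no figure for overlap.

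**1. Steps and sleep (algebra).** If the crossing day is one of m valid baseline days:

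change = ((m − 1)/m) × (crossing-day value − mean of the other baseline days).

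The shrinkage is 1/m: 7.1% for m = 14, 14.3% for m = 7, 50% for m = 2, and 100% for m = 1. If h of 14 baseline days, including the crossing day, carry the same true shift, the shrinkage is h/14: 21% for h = 3, 36% for h = 5, 50% for h = 7.

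**2. MIF bound (algebra).** If the crossing day is in Days 1–14, change = best of that day − best of a set containing that day, which is at most 0. The bound does not apply to volume, duration or time to MIF. It also does not apply under the no-use fallback, where the first crossing is necessarily after Day 14.

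**3. MIF with no true change (illustration).** Assume independent normal breaths, 3 on a usual day and 6 on the crossing day. Expected maxima in SD units are 1.27 for 6 breaths, 2.18 for 42 and 2.21 for 45.

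- Crossing day inside the window (13 × 3 + 6 = 45 baseline breaths): 1.27 − 2.21 = −0.94 SD, never positive.
- Crossing day outside (14 × 3 = 42): 1.27 − 2.18 = −0.91 SD, positive with probability 6/48 = 12.5%.

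Overlap therefore adds about 0.03 SD. A second illustration, at an average of 5 inhalations per day, gives −1.06 inside and −1.07 outside.

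**4. How often the first crossing falls in Days 1–14.** With k exceedance days placed at random among 84, the probability is 1 − C(70,k)/C(84,k): 17% (k = 1), 31% (2), 43% (3), 52% (4), 78% (8). A majority needs about 4 or more such days.

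Simulation: patient means gamma or lognormal with the protocol 3.3 means and SDs, 20% or 25% from the exacerbating group, daily counts Poisson or overdispersed, the latter with or without day-to-day correlation, no trend, 84 days.

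| Threshold | Of patients who ever exceed it | Of all patients |
|---|---|---|
| >4 | 56–80% | 31–58% |
| >12 | 44–75% | 7–29% |
| >20 | 40–75% | 3–19% |

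**The case against.** The strongest reply is that little depends on these tables. They are descriptive, carry no test or decision rule, and print actual values beside the changes. The tested flow comparison in SAP 7.5.2.1 uses two adjacent pre-CAE weeks and not this baseline. Steps and sleep come from planned subsets of about 100 patients each. All of that stands and limits the weight of the point.

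A reader might infer more than the documents support:

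- **That most patients are affected.** The documents give no frequency. The simulated majority applies only to patients who exceed 4. The ranges for >12 and >20 cross 50%, and as shares of all patients they are minorities. The usage figures come from another cohort, and the no-trend assumption sits uneasily with the hypothesis that use rises before a CAE.
- **That overlap causes the apparent fall in MIF.** It causes the cap at zero, but almost none of the average shift: −0.94 SD inside against −0.91 SD outside.
- **That step and sleep changes are muted by a quarter to a half or more.** This needs every high-use baseline day to carry the full shift. It can also be argued that frequent high-use days are part of a heavy user's usual state, which is what the SAP's baseline describes. The crossing day alone costs about 7% with complete data.
- **That no other analysis links albuterol use with these measures.** Protocol 9.5.2.1 plans models that combine them, and SAP 7.5.3 assigns the predictive work to the data analytics group.

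**Conclusion.** The concern holds in a limited form. The SAP lets the first >4, >12 or >20 day sit inside its own baseline. When it does, MIF change cannot be positive, and step and sleep change shrinks by at least 1/m, about 7% with 14 valid days. These two results follow from the definitions alone. Larger shrinkage requires other baseline days with a similar shift.

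Under usage assumptions borrowed from the cohort in protocol 3.3, overlap affects a majority of patients who exceed 4. Whether it does so for >12 and >20 is uncertain. Any distortion of the comparison by CAE status is plausible in direction, but its size on these tables has not been established.

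The downward shift in MIF, about 0.9 SD of a breath in an illustration with no true change, is a separate fault. It comes from unequal maxima and would remain if the overlap were removed. Since the tables are descriptive and show actual values, correcting them is a modest improvement and not a condition for the study's conclusions.

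**What to change.** Change only the threshold-day tables in SAP 7.2.2.1, 7.3.2.1 and 7.4.2.1.

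- **Steps and sleep:** take as reference the mean over the patient's Day 1–14 days at or below the threshold in question, always excluding the crossing day. Report how many patients have no reference.
- **Flow:** compare like with like. Use the mean of the day's inhalations, or the first inhalation of the day, on both the crossing day and the reference days. Use only days with actual inhalations and no carried-forward values.
- **Reporting:** state how many first crossings fall in Days 1–14, by CAE status.

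Two simpler repairs work less well. Restricting the tables to crossings after Day 14 leaves the MIF shift at −0.91 SD and, with gamma-distributed use at the two cited levels, loses 76–87% of patients who exceed 4. Keeping daily best MIF but comparing it with the average daily best on low-use days reverses the artefact, because the crossing day has more breaths: 1.27 − 0.85 = +0.42 SD in the illustration above (0.85 is the expected maximum of 3 breaths).

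The cost is SAP wording and programming, with no new data. Some persistent heavy users have no low-use reference days and leave the change columns, although their actual values are still shown. If at least 3 reference days were required, the loss among patients who exceed 4 would be about 3–45% under the same gamma assumptions. Looking only at days before the crossing, with the same minimum, would lose about 48–72%.

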7.2.2.2. Actual and Change from Baseline in Week *Y* Inhalational Flow Values

Summary descriptive statistics of the actual inhalational flow values and change from baseline in MIF, inhalational volume, inhalation duration, and time to MIF for each study week (1 through 12) will be presented overall, and by CAE status and by CAE severity.

7.3. Accelerometry: Total Daily Steps

7.3.1. Total Daily Steps Definition

Study Day *X* and Week *Y* TDS are defined as follows:

Study Day *X* TDS: The TDS for Study Day *X* are the TDS recorded by accelerometry on Study Day *X*.

Week *Y* TDS: The TDS for Week *Y* are computed using the set of TDS taken by the patient during a given week on study. The average will be calculated as the sum of the daily TDS divided by the number of days with nonmissing TDS.

The TDS are computed for those patients in the ankle accelerometry analysis set.

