APPENDIX B. STUDY PROCEDURES AND ASSESSMENTS BY VISIT

1. Procedures During Screening Visit (Visit 1, Day -14 to Day 1)

The screening visit (visit 1) will take place not more than 2 weeks before the baseline visit (visit 2) and may occur at the same time as the baseline visit (visit 2). The following procedures will be performed at visit 1:

- obtain written informed consent before any study-related procedures are performed
- review inclusion and exclusion criteria
- assign patient number
- obtain medical history
- obtain prior medication and treatment history
- physical examination, including height and weight
- vital signs measurements, including blood pressure, respiratory rate, and heart rate
- urine pregnancy test for women of childbearing potential
- complete ACQ-5
- inform patients of study compliance for multidose dry powder inhaler with an eModule (eMDPI) and accelerometer, and requirement for provider visit in the event of a clinical asthma exacerbation (CAE)
- assess for asthma exacerbations
- prior and concomitant medication inquiry

2. Procedures During Intervention Period

a. Baseline Visit (Visit 2, Day 1)

Patients who meet the inclusion and exclusion criteria at visit 1 may continue to visit 2, when baseline assessments will be conducted (visits 1 and 2 may be combined).

The following procedures will be performed at visit 2:

- review inclusion and exclusion criteria
- inform patients of study compliance for eMDPI and accelerometer, and requirement for provider visit in the event of a CAE
- assess for asthma exacerbations
- inquire about adverse events
- train on use of wearable accelerometers and dispense to the subset of patients who consent to using the devices
- train on the use, collection and accountability of inhaler and dispense albuterol sulfate (ABS) eMDPI

• concomitant medication inquiry

b. Phone Visit (Visits 3 and 4, Days 28±7 days and 56±7 days, respectively)

Patients will be contacted by phone on a monthly basis between visit 2 and visit 3.

The following information will be discussed during the phone call:

- assess for asthma exacerbations and treatments
- inquire about adverse events
- concomitant medication inquiry
- ABS eMDPI dispense, training, collection, and accountability (only Visit 3)
- inform patients of study compliance for eMDPI and accelerometer, and requirement for a provider visit in the event of CAE

c. Final Visit/Early Termination Visit (Visit 5, Day 84 [±14 days])

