^c Vital signs measurements will include blood pressure, respiratory rate, and heart rate (pulse rate).

^d Wearable accelerometers for a subset of patients who consent to participate at specific sites will be dispensed at visit 2 and SDI and TDS data will be collected continuously from visit 2 through visit 5 via the wearable accelerometer. Instructions for proper use of the devices will be provided to patients at visit 2. The devices will be collected at visit 5.

^e Patients will receive initial ABS eMDPI devices at visit 2 and subsequently by courier on Day 21. Patients will be instructed to return all inhalers to the site at the last study visit or early termination. Instructions for dispensing, proper clinical use, and collecting ABS eMDPI will be provided to patients at visit 2 and reviewed during the monthly calls.

ABS=albuterol sulfate; CAE=clinical asthma exacerbation; SDI=sleep disruption index; TDS=total daily steps; eMDPI=multidose dry powder inhaler with an eModule; IMP=investigational medicinal product; V=visit. Screening and baseline visits may be combined.

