3.5. Ankle Accelerometry Analysis Set

The ankle accelerometry analysis set is a subset of the mITT analysis set that will include patients who wore an ankle accelerometer with sufficient memory to capture 12 weeks of data during study participation and for whom data from the ankle accelerometer were successfully downloaded at the end of the study.

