4.2.5. Sleep Parameters

There are 8 measures of sleep disruption: (i) nighttime average total time in bed, (ii) nighttime average total sleep time, (iii) nighttime average sleep latency time, (iv) nighttime average wakening after sleep onset, (v) total time awake at night, (vi) daytime average minutes asleep, (vii) longest daytime sleep episode and (viii) longest nighttime wake episode. The first 7 sleep parameters are provided via Philips accelerometry and longest nighttime wake episode is derived from the accelerometry data as follows:

The sleep interval data provided via Philips accelerometry includes the activity state ("sleep"/"awake") every 30 seconds during the sleep interval. The number of successive 30 second "awake" states occurring between "sleep" states within the sleep interval is summed to determine the duration of a given "awake" state. The longest nighttime wake episode is the summated "awake" state with the longest duration during the sleep interval.

The baseline value of a given sleep parameter (eg, nighttime average total time in bed) is the average sleep parameter (eg, nighttime average total time in bed), computed using the sleep parameter (eg, nighttime average total time in bed) values captured by accelerometry during study day 1 through day 14. The average will be calculated as the sum of the average sleep parameter divided by the number of days with nonmissing values of the average sleep parameter. If no sleep parameter data are available for study day 1 through study day 14, the 'baseline value of a given sleep parameter' is the first available valid sleep parameter value after study day 14.

Baseline sleep parameters are computed for those patients in the wrist accelerometry analysis set.

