4.5. Study Day and Study Week

Study days will be numbered relative to the earliest date an ABS eMDPI device was dispensed (ie, ... -2, -1, 1, 2, ...). Day 1 is defined as the earliest date an ABS eMDPI device was dispensed and Day -1 is the day before the first ABS eMDPI device was dispensed.

Week I is defined as study day $(j + 1)$ to study day $(j + 7)$, inclusive where $I = 1$ to 12 and $j = 0, 7, 14, 21, 28, 35, 42, 49, 56, 63, 70, 77, 84$, respectively.

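### Step averages have no wear condition or minimum day count, so reduced wear can read as reduced activity; separately, the part-day of dispensing biases the step baseline low

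*SAP*

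**What the plan says.** **Daily value.** The steps for Study Day X "are the TDS recorded by accelerometry on Study Day" X (SAP 7.3.1). No minimum wear time is attached.

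**Weekly value.** "The average will be calculated as the sum of the daily TDS divided by the number of days with nonmissing TDS" (SAP 7.3.1). Nonmissing is not defined in terms of wear, and one day is enough for a weekly value.

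**Baseline.** This is an average "computed using the daily steps recorded during the first 14 days of study participation (study day 1 through study day 14"), again over nonmissing days (SAP 4.2.4). "Day 1 is defined as the earliest date an ABS eMDPI device was dispensed" (SAP 4.5). Protocol Appendix B places accelerometer dispensing at that same visit: "train on use of wearable accelerometers and dispense to the subset of patients who consent to using the devices". SAP Table 1, footnote d, adds that "SDI and TDS data will be collected continuously from visit 2 through visit 5". Day 1 recording therefore starts part-way through the day, and Day 1 is in the baseline.

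**Entry to the analysis set.** A patient must have worn an ankle device with sufficient memory and be one "for whom data from the ankle accelerometer were successfully downloaded at the end of the study" (SAP 3.5). SAP 3.4 has the same condition for the wrist. A failed download is the only cause of missing accelerometer data that SAP 4.6 names.

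**Sleep.** "The sleep interval data provided via Philips accelerometry includes the activity state" for each 30 seconds (SAP 4.2.5). Seven of the eight sleep measures come directly from the device. How off-wrist time is scored is not described. The word *valid* appears once, in the rule for a missing sleep baseline, and is not defined. The weekly longest wake episode is a maximum over nights and is one of the three terms summed into the SDI composite (SAP 7.4.1).

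**The concern.** Protocol 2.1.1 brings in daily steps as a correlate of dyspnea on exertion, so a fall in steps is the signal of interest. Taking the ankle device off for part of a day also produces a fall. The SAP's rules cannot tell the two apart, because a partly worn day has a value and enters every average with full weight.

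The tables affected are steps before the CAE symptom peak, the maximum change from baseline, and change from baseline by study week (SAP 7.3.2.1 and 7.3.2.2). The maximum change is exposed most. It is an extreme over days with no sign defined, and if it is read as the largest fall, one poorly worn day can set a patient's value. The pre-peak tables rest on few events in a subset of 100 patients, so a few such days can move a mean.

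Including Day 1 is a second error of a different kind. It lowers the reference value, and from Week 2 on it works against the first error.

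**Working it through.** **Plan figures used.** 360 / (1 − 0.10) = 400 enrolled; 360 × 0.20 = 72 and 360 × 0.25 = 90 CAEs. Both agree with SAP 2.3 and are not in dispute. For a subset of 100 with 10% dropout, 90 × 0.20 = 18 to 90 × 0.25 = 22.5 patients with a CAE; with all 100 counted, 20 to 25.

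**Assumptions.** The documents give no wear data. True activity is held constant, and f is the share of a normal day's steps that is recorded on a given day.

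**1. Weekly mean, one affected day.** Ratio = (6 + f)/7.
- Half the steps recorded (f = 0.5): 6.5/7 = 0.929, or −7.1%. This needs no assumption about how unworn days are output.
- Fully unworn and output as zero (f = 0): 6/7 = 0.857, or −14.3%.
- Fully unworn and output as missing: 6/6, no change.

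**2. Day 1 in the baseline.** Ratio = (13 + f)/14 with 14 days of data. Unchanged activity then reads as 14/(13 + f) − 1.

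| f on Day 1 | Baseline error | Unchanged activity from Week 2 on reads as |
|---|---|---|
| 0.75 | −1.8% | +1.8% |
| 0.50 | −3.6% | +3.7% |
| 0.25 | −5.4% | +5.7% |

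Because no minimum applies, the error grows as days are lost. With 3 usable days including Day 1 and f = 0.5 it is 2.5/3 − 1 = −16.7%.

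Week 1 (days 1 to 7) also contains Day 1, so with f = 0.5 its change from baseline is (6.5/7)/(13.5/14) − 1 = −3.7%. Later weeks read +3.7%. One part-day thus creates an apparent rise after Week 1.

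**3. Both errors together, a later week, f = 0.5 on Day 1.**
- One half-recorded day: (6.5/7)/(13.5/14) − 1 = −3.7%.
- One zero-coded day: (6/7)/(13.5/14) − 1 = −11.1%.

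**4. Return date.** Visit 5 is Day 84 ± 14, that is Day 70 to 98, so the return date can fall inside Weeks 10 to 12. If the device is returned on Day 71, the Week 11 value (days 71 to 77) is that single part-day; with f = 0.5 it is 50% low.

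**5. Table for 1 day before the peak.** Take 20 CAEs with equal baselines. Each half-recorded day shifts the mean change by 0.5/20 = 2.5% of baseline; each zero-coded day shifts it by 1/20 = 5%.

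**6. Sleep.** No size can be given for an unworn night, because its scoring is not described. One direction does follow from the definitions. A maximum over fewer nights cannot exceed the maximum over all seven. If nights are exchangeable and 4 of 7 are recorded, the night that would set the weekly maximum is absent with probability 3/7 = 43%.

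**The case against.** The strongest reply is that the SAP may already treat unworn days as missing. Within a set that requires a successful download, SAP 4.2.4 and 4.6 still provide for a patient with no step data on days 1 to 14, and the averages divide by nonmissing days. Missing days inside a downloaded record are therefore expected. This stands as far as it goes. A reader might infer that a day on the bedside table counts as zero steps, but the documents do not say so, and the 14.3% figure is conditional. The reply does not reach partly worn days, which have a value and are low.

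A reader might also infer that an unworn wrist device scores as good sleep. That is not supported. Off-wrist scoring is not described, the longest wake episode is counted only between sleep states inside a device-supplied sleep interval, and an undefined notion of a valid sleep value exists. An unworn night could be missing, low or high.

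Two further inferences lack a source: that wear declines over the study, and that patients take the device off as an exacerbation approaches. Neither document says either. The pre-peak tables cover 1 to 21 days before the peak, so removal on or after the peak day does not enter them.

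It is also fair that every step and sleep analysis left in the SAP is descriptive. The within-patient tests in SAP 7.5.2.1 use neither measure, and prediction is passed to the data analytics group (SAP 7.5.3). Device compliance is reinforced at visits 1 to 4, and a User Guide not seen here covers wear. These points limit the consequence. They do not supply a rule for the SAP's own tables, since the separate report only may give details.

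**Conclusion.** The concern holds for steps. Followed exactly, SAP 4.2.4 and 7.3.1 count a partly worn day as a full day, and reduced wear can be misread as reduced activity. The size is 7.1% of a 7-day mean for each day with half the usual steps. It is 14.3% for a fully unworn day only if that day is output as zero.

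Separately, the dispensing day makes the step baseline too low, by about 3.6% if half of Day 1 is recorded and all 14 days have data. From Week 2 on this raises the change from baseline by about 3.7% and partly masks a true fall, so it should not be read as adding to the spurious fall.

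For sleep, what can be said is that the effect of non-wear on SDI is undefined, and that the weekly longest wake episode tends to be lower when fewer nights are recorded. The Day 1 point concerns steps, since the first night may be complete.

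All sizes rest on assumed recording shares and constant true activity. The tables affected are descriptive, so this is a matter of correct interpretation and does not threaten a planned test.

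**What to change.** Amend SAP 4.2.4, 4.2.5, 7.3.1 and 7.4.1 as follows.

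- Start the step baseline on Day 2, leave Day 1 out of the Week 1 step value, and drop the device return date.
- State how the device output codes non-wear for steps and for sleep.
- Set steps or sleep values to missing on any day or night that fails a prespecified wear criterion, for example at least 10 hours of wear for steps and wear through the sleep interval for sleep.
- Require a minimum number of valid days or nights, for example 7 of 14 for baseline and 4 of 7 for a weekly value. These thresholds are proposals; the documents give no basis for particular values. What matters is that they are fixed in advance.
- Report the number of valid days by week, by CAE status, and in the 7 days before the peak.

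The cost is SAP wording and one derivation from data already downloaded. Some patient-days and a few CAEs will leave the step and sleep tables, which matters with about 18 to 25 CAE patients per subset. The loss may also be selective: a rule that treats long runs of zero activity as non-wear could remove truly inactive days before a CAE, which are the signal sought. Show the tables with and without the exclusion so that the reader can judge this.
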